Appendix 4. Common Terminology Criteria for Adverse Events (CTCAE) v 4.03

CTCAE v4.03 can be accessed from the below link:

http://evs.nci.nih.gov/ftp1/CTCAE/CTCAE_4.03_2010-06-14_QuickReference_8.5x11.pdf

The only modification to the CTCAE criteria is the addition of a Grade 1 upper respiratory infection as follows:

CTCAE v4.0 Term	Grade 1	Grade 2	Grade 3	Grade 4	Grade 5	CTCAE v4.03 AE Term Definition
Upper respiratory infection	Mild symptoms; symptomatic relief (eg, cough suppressant, decongestant)	Moderate symptoms; oral intervention indicated (eg, antibiotic, antifungal, antiviral)	IV antibiotic, antifungal, or antiviral intervention indicated; radiologic, endoscopic, or operative intervention indicated	Life-threatening consequences; urgent intervention indicated	Death	A disorder characterized by an infectious process involving the upper respiratory tract (nose, paranasal sinuses, pharynx, larynx, or trachea).

## LIST OF ABBREVIATIONS

AE	adverse event
ANOVA	analysis of variance
AUC	area under the curve
BLQ	below the limit of quantitation
BMI	body mass index
CI	confidence interval
CLcr	creatinine clearance
CRF	case report form
CSR	clinical study report
CTCAE	Common Terminology Criteria for Adverse Events
CV	coefficient of variation
ECG	Electrocardiogram
eCRF	electronic case report form
eGFR	estimated glomerular filtration rate
ET	early termination
GLSM	geometric least squares mean
HBV	hepatitis B virus
HCV	hepatitis C virus
HIV	human immunodeficiency virus
ID	Identification
LLOQ	lower limit of quantitation
LOQ	limit of quantitation
MDRD	Modification of Diet in Renal Disease
MedDRA	Medical Dictionary for Regulatory Activities
PD	Pharmacodynamics
PK	pharmacokinetic(s)
PT	prothrombin time
PT	preferred term
Q1	first quartile
Q3	third quartile
SAE	serious adverse event
SAP	statistical analysis plan
SD	standard deviation
SE	standard error
SOC	system organ class
WHO	World Health Organization

## PHARMACOKINETIC ABBREVIATIONS AND DEFINITIONS

$AUC_{last}$	area under the plasma/serum concentration versus time curve from time zero to the last quantifiable concentration
$AUC_{inf}$	area under the plasma/serum concentration versus time curve extrapolated to infinite time, calculated as $AUC_{last} + (C_{last}/\lambda_z)$
$\%AUC_{exp}$	percentage of AUC extrapolated between $AUC_{last}$ and $AUC_{inf}$
$C_{max}$	maximum observed plasma/serum concentration of drug
$C_{last}$	last observed quantifiable plasma/serum concentration of the drug
$CL/F$	apparent oral clearance after administration of the drug: $CL/F = Dose/AUC_{inf}$ , where “Dose” is the dose of the drug
$\lambda_z$	terminal elimination rate constant, estimated by linear regression of the terminal elimination phase of the log plasma/serum concentration of drug versus time curve of the drug
$T_{max}$	time (observed time point) of $C_{max}$
$T_{last}$	time (observed time point) of $C_{last}$
$t_{1/2}$	estimate of the terminal elimination half-life of the drug in plasma/serum, calculated by dividing the natural log of 2 by the terminal elimination rate constant ( $\lambda_z$ )
$V_z/F$	apparent volume of distribution of the drug
$A_e$	Amount of unchanged drug excreted in urine calculated either over a specific interval ( $A_{e(interval)}$ ) or cumulatively over all collection intervals, calculated as (Concentration of unchanged drug in urine) · (Volume of urine collected)
$CL_r$	The renal clearance of unchanged drug in a specific interval ( $CL_{r(interval)}$ ) or cumulatively over all collection intervals
$\% Dose_{excreted}$	The percentage of given dose excreted in the urine as unchanged drug

## 1. INTRODUCTION

This statistical analysis plan (SAP) describes the statistical analysis methods and data presentations to be used in tables, figures, and listings in the clinical study report (CSR) for Study GS-US-379-1932. This SAP is based on the study protocol amendment 1 dated 9 January 2017, and the electronic case report form (eCRF). The SAP will be finalized before database finalization. Any changes made after the finalization of the SAP will be documented in the CSR.

### 1.1. Study Objectives

The primary objective of this study is as follows:

- To evaluate the pharmacokinetics (PK) of GS-9876 in subjects with impaired renal function relative to matched, healthy controls

The secondary objective of this study is as follows:

- To evaluate the safety and tolerability of GS-9876 in subjects with normal and impaired renal function

### 1.2. Study Endpoints

The primary endpoints are PK parameters  $AUC_{last}$ ,  $AUC_{inf}$ , and  $C_{max}$  for GS-9876.

The secondary endpoints include the incidence of adverse events (AEs), laboratory abnormalities, vital sign changes and safety ECG abnormalities.

### 1.3. Study Design

Study GS-US-379-1932 is an open-label, parallel-group, adaptive, single-dose, multi-center Phase 1 study to evaluate the PK of GS-9876 in subjects with impaired renal function.

This study will target enrolling 20 to 60 subjects using an adaptive design that includes up to 3 enrolled cohorts of subjects with renal impairment and matched healthy controls. Based on safety and PK results from subjects with moderate renal impairment (Cohort 1), subjects with severe renal impairment (Cohort 2) and/or mild renal impairment (Cohort 3) will be enrolled as follows:

[figure not shown]
- Cohort 1 (Moderate Renal Impairment): Up to 20 subjects (10 per group, moderate renal impairment and matched healthy controls) for 8 evaluable subjects per group.
- Adaptive Cohort 2 (Severe Renal Impairment): Up to 20 subjects (10 subjects with severe renal impairment and up to 10 matched healthy control subjects if none of the healthy subjects from a previous cohort is an appropriate match for a severe impairment subject) for 8 evaluable subjects per group.

- Adaptive Cohort 3 (Mild Renal Impairment): Up to 20 subjects (10 subjects with mild renal impairment and up to 10 matched healthy control subjects if none of the healthy subjects from a previous cohort is an appropriate match for a mild impairment subject) for 8 evaluable subjects per group.

Adaptive Cohorts 2 and/or 3 will be enrolled as determined by safety and/or PK data in Cohort 1. Specifically, Cohort 2 (Severe Renal Impairment) will be evaluated if supported by safety and/or PK data from Cohort 1 (Moderate Renal Impairment). Cohort 3 (Mild Renal Impairment) will be evaluated if supported by safety and if substantial changes ( $\geq 2$ -fold mean difference from matched controls) in the exposure of GS-9876 is observed in subjects with moderate renal impairment in Cohort 1. Cohorts 2 and 3 may not be enrolled or may be enrolled sequentially or in parallel, as governed by safety and PK data in Cohort 1. Each control subject may be matched to multiple renal impaired subjects across different cohorts and can be matched to only 1 renal impaired subject within a cohort.

An overview of the study design is shown in [Figure 1-1](#).

**Figure 1-1. Study Design**

The categorization of renal impairment is based on creatinine clearance (CLCr) using the Cockcroft-Gault formula from the screening visit. Specifically, a subject will be considered as having

[figure not shown]
- Mild impairment if CLcr (rounding to the nearest integer) is 60-89 mL/min
- Moderate impairment if CLcr (rounding to the nearest integer) is 30-59 mL/min
- Severe impairment if CLcr (rounding to the nearest integer) is 15-29 mL/min

A subject with CLcr (rounding to the nearest integer) higher than or equal to 90 mL/min is categorized as having normal renal function.

Following screening and Day -1 procedures, eligible subjects will be confined to the study center beginning Day -1 until the completion of assessments on Day 6. Subjects will return 14 ( $\pm$ 1) days after last dose for an in-clinic follow up visit (ie, Day 15).

The study schema is shown in [Figure 1-2](#).

**Figure 1-2. Study Schema**

- ▲ GS-9876 20 mg
- █ Clinic Confinement
- X Intensive PK Samples
- ➡ Discharge
- ‡ Matched healthy control subjects will begin dosing after completion of PK assessments (Day 6) for the subject with renal impairment.

## **Pharmacokinetic Assessments**

### **Plasma PK Assessment**

Plasma concentrations of GS-9876 will be measured and PK parameters determined. Plasma concentrations of GS-9876 metabolites may be determined and pharmacokinetics explored, as applicable.

Intensive PK sampling will occur relative to dosing of GS-9876 at the following time points:

- Day 1: 0 (predose), 0.5, 1, 2, 3, 4, 5, 6, 8, 12, 16, 24, 36, 48, 60, 72, 96 and 120 hours postdose

### **Urine PK Assessment**

Urine PK samples will be collected relative to dosing of GS-9876 at the following intervals:

- Day 1: Pre-dose void, 0-6, 6-12, 12-24, 24-48, 48-72, 72-96 and 96-120 hours postdose

Urine concentrations of GS-9876 and/or metabolites may be determined and PK parameters estimated.

### **Protein Binding Assessment**

Protein binding of GS-9876 (and its metabolites, as applicable) will be assessed at or near their  $T_{max}$  timepoint(s) as well as another later time point.

## **Safety Assessments**

Safety will be evaluated by assessment of clinical laboratory tests, electrocardiogram (ECG), periodic physical examinations including vital signs at various time points during the study, and by documentation of adverse events (AEs).

Complete physical exam: Screening, Days -1, 6, and at the follow-up visit 14 ( $\pm$ 1) days after last dose or at the Early Termination (ET) visit, if applicable

Symptom driven physical exam: every day during confinement as needed, based on reported signs and symptoms

Height: Screening

Weight: Screening and Day -1

Urine Drug and Alcohol Assessments: Screening, Day -1

Serology Test (hepatitis B virus [HBV], hepatitis C virus [HCV], human immunodeficiency virus [HIV]): Screening

Serum Pregnancy Test (women of childbearing potential only): Screening, Day -1, 6, and at the follow-up visit 14 ( $\pm 1$ ) days after last dose or at the ET visit, if applicable

Vital signs (blood pressure, pulse, respiration rate, and temperature): Screening, Days -1, 1 (predose, 1, 3, 6, and 12 hours postdose), 2, 3, 4, 5, 6, and at the follow-up visit 14 ( $\pm 1$ ) days after last dose or at the ET visit, if applicable

Clinical laboratory tests (blood chemistry, and urinalysis): Screening, Days -1, 1 (4 hours postdose), 2, 3, 6, and at the follow-up visit 14 ( $\pm 1$ ) days after last dose or at the ET visit, if applicable

Clinical laboratory tests (hematology and coagulation): Screening, Days -1, 1 (4 hours postdose), 3, 6, and at the follow-up visit 14 ( $\pm 1$ ) days after last dose or at the ET visit, if applicable.

12-lead ECG: Screening, Days -1, 1 (postdose), 6, and at the follow-up visit 14 ( $\pm 1$ ) days after last dose or at the ET visit, if applicable

Assessment of AEs and concomitant medications will continue throughout the study.

#### **1.4. Sample Size and Power**

With 16 (8 per group) evaluable subjects, the estimated two-sided 90% CI of the GLSM ratio of test versus reference groups, with regards to PK parameters (AUC and  $C_{\max}$ ) would be within (50%, 200%) with over 95% probability. This calculation is based on a two group t-test of equivalence in means at the significance level of 0.05, assuming the expected geometric means ratio of 1.0 and inter-subject standard deviation (SD) of no more than 0.35 on a natural logarithm scale. The assumption about the inter-subject SD is supported by previous Gilead study GS-US-379-1372 using the maximum variability for AUC and  $C_{\max}$  from the closest dose levels (15 mg and 30 mg) of the dose in this study. An overage of 2 subjects per group will be enrolled to accommodate subject drop-outs, thus requiring a total enrollment of 20 subjects (10 per group) for each cohort.

## **2. TYPE OF PLANNED ANALYSIS**

### **2.1. Data Monitoring Committee**

This study does not have a data monitoring committee.

### **2.2. Interim Analysis**

No formal interim analyses are planned for this study.

### **2.3. Final Analysis**

After all subjects have completed the study, outstanding data queries have been resolved or adjudicated as unresolvable,, and the database has been cleaned and finalized, the final analysis of the data will be performed.

### **2.4. Changes from Protocol-Specified Analysis**

No changes from protocol-specified analyses are planned.

### **3. GENERAL CONSIDERATIONS FOR DATA ANALYSES**

Analysis results will be presented using descriptive statistics. For categorical variables, the number and percentage of subjects in each category will be presented; for continuous variables, the number of subjects, mean, SD or standard error (SE), median, first quartile (Q1), third quartile (Q3), minimum, and maximum will be presented.

By-subject listings will be presented for all subjects in the All Enrolled Analysis Set, and sorted by subject identification (ID) number in ascending order, visit date, and time (if applicable), unless otherwise specified. Data collected on log forms, such as AEs, will be presented in chronological order within subject. Age, sex at birth, race, and ethnicity will be included in the listings, as space permits.

#### **3.1. Analysis Sets**

Analysis sets define the subjects to be included in an analysis. Analysis sets and their definitions are provided in this section. The analysis set will be identified and included as a subtitle of each table, figure, and listing.

For each analysis set, the number and percentage of subjects eligible for inclusion will be provided in the disposition table as detailed in Section 4.

##### **3.1.1. All Enrolled Analysis Set**

The All Enrolled Analysis Set includes all subjects who received a study subject ID number in the study after screening.

This is the primary analysis set for listings.

##### **3.1.2. Safety Analysis Set**

The Safety Analysis Set includes all enrolled subjects who received GS-9876. This is the primary analysis set for safety tables.

##### **3.1.3. Pharmacokinetic Analysis Set**

The PK Analysis Sets include all enrolled subjects who took study drug and have at least 1 nonmissing postdose concentration value reported by the PK laboratory for the corresponding analytes. These are the primary analysis sets for all PK analyses.

#### **3.2. Strata and Covariates**

This study does not use a stratified randomization schedule in enrolled subjects. No covariates will be included in analyses.

### **3.3. Examination of Subject Subsets**

There are no prespecified subject subsets for analyses.

### **3.4. Multiple Comparisons**

All endpoint tests will be done at the significance level of 0.05 with no multiplicity adjustments.

### **3.5. Missing Data and Outliers**

#### **3.5.1. Missing Data**

In general, missing data will not be imputed unless methods for handling missing data are specified.

The handling of missing or incomplete dates for AE onset is described in Section [7.1.6.2](#).

#### **3.5.2. Outliers**

Outliers of non-PK data will be identified during the data management and data analysis process, but no sensitivity analyses will be conducted. All data will be included in the data analysis.

### **3.6. Data Handling Conventions and Transformations**

In general, age (in years) on the date of the first dose of study drug will be used for analyses and presentation in listings. If an enrolled subject was not dosed with any study drug, the enrollment date will be used instead of the first dosing date of study drug. If only the birth year is collected on the CRF, “01 July” will be used for the unknown birth day and month for the purpose of age calculation. If only birth year and month are collected, “01” will be used for the unknown birth day.

Non-PK data that are continuous in nature but are less than the lower limit of quantitation (LOQ) or above the upper LOQ will be imputed as follows:

- A value that is 1 unit less than the LOQ will be used to calculate descriptive statistics if the datum is reported in the form of “< x” (where x is considered the LOQ). For example, if the values are reported as < 50 and < 5.0, values of 49 and 4.9, respectively, will be used to calculate summary statistics. An exception to this rule is any value reported as < 1 or <0.1, etc. For values reported as < 1 or < 0.1, a value of 0.9 or 0.09, respectively, will be used to calculate summary statistics.
- A value that is 1 unit above the LOQ will be used to calculate descriptive statistics if the datum is reported in the form of “> x” (where x is considered the LOQ). Values with decimal points will follow the same logic as the bullet point above.
- The LOQ will be used to calculate descriptive statistics if the datum is reported in the form of “≤ x” or “≥ x” (where x is considered the LOQ).

If methods based on the assumption that the data are normally distributed are not adequate, analyses may be performed on transformed data or nonparametric analysis methods may be used, as appropriate.

Natural logarithmic transformation will be used for analyzing concentrations and PK parameters. Concentration values that are below the limit of quantitation (BLQ) will be presented as “BLQ” in the concentration data listing. Values that are BLQ will be treated as 0 at predose time points, and one-half the value of the lower limit of quantitation (LLOQ) at postdose time points for determination of summary and order statistics.

The following conventions will be used for the presentation of summary and order statistics:

- If at least 1 subject has a concentration value of BLQ for the time point, the minimum value will be displayed as “BLQ.”
- If more than 25% of the subjects have a concentration data value of BLQ for a given time point, the minimum and Q1 values will be displayed as “BLQ.”
- If more than 50% of the subjects have a concentration data value of BLQ for a given time point, the minimum, Q1, and median values will be displayed as “BLQ.”
- If more than 75% of the subjects have a concentration data value of BLQ for a given time point, the minimum, Q1, median, and Q3 values will be displayed as “BLQ.”
- If all subjects have concentration data values of BLQ for a given time point, all order statistics (minimum, Q1, median, Q3, and maximum) and summary statistics will be displayed as “BLQ.”

Pharmacokinetic parameters that are BLQ will be imputed as one-half LOQ before log transformation or statistical model fitting.

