8.1.2. Primary Endpoint

The primary endpoints are PK parameters AUC_{last} , AUC_{inf} , and C_{max} for GS-9876.

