8.8. Sample Size

With 16 (8 per group) evaluable subjects, the estimated two-sided 90% CI of the GLSM ratio of test versus reference groups, with regards to PK parameters (AUC and C_{max}) would be within (50%, 200%) with over 95% probability. This calculation is based on a two group t-test of equivalence in means at the significance level of 0.05, assuming the expected geometric means ratio of 1.0 and inter-subject SD of no more than 0.35 on a natural logarithm scale. The assumption about the inter-subject SD is supported by previous Gilead study GS-US-379-1372 using the maximum variability for AUC and C_{max} from the closest dose levels (15 mg and 30 mg) of the dose in this study. An overage of 2 subjects per group will be enrolled to accommodate subject drop-outs, thus requiring a total enrollment of 20 subjects (10 per group) for each cohort.

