## 8.2. Statistical Analysis Methods

### 8.2.1. General considerations

Individual subject concentration data and individual subject PK parameters including percentage of protein binding for GS-9876 will be listed and summarized using descriptive statistics by renal function group. Summary statistics (numbers of subjects, mean, SD, coefficient of variation, median, minimum, maximum, Q1, and Q3) will be presented for both individual subject concentration data by time point and individual subject PK parameters by renal function group. Moreover, the geometric mean, 95% CI, and the mean and SD of the natural log-transformed values will be presented for individual subject PK parameter data.

Individual concentration data listings and summaries will include all subjects with concentration data. The sample size for each time point will be based on the number of subjects with nonmissing concentration data at that time point. The number of subjects with concentration BLQ will be presented for each time point. For summary statistics, BLQ values will be treated as zero at predose and one-half of the LLOQ for postdose time points.

Individual PK parameter data listings and summaries will include all subjects for whom PK parameter(s) can be derived. The sample size for each PK parameter will be based on the number of subjects with nonmissing data for that PK parameter.

In addition to the renal function categorization based on CLcr throughout this study, MDRD-based eGFR will be used for subject categorization in PK analysis. Subjects from all cohorts will be pooled and regrouped according to their MDRD-based eGFR values as follows:

- Normal renal function if eGFR (rounding to the nearest integer) is  $\geq 90$  mL/min/1.73m^2
- Mild impairment if eGFR (rounding to the nearest integer) is 60-89 mL/min/1.73m^2
- Moderate impairment if eGFR (rounding to the nearest integer) is 30-59 mL/min/1.73m^2

- Severe impairment if eGFR (rounding to the nearest integer) is 15-29 mL/min/1.73m^2
- End stage renal impairment if eGFR (rounding to the nearest integer) is  $\leq 14$  mL/min/1.73m^2

The following tables will be provided for GS-9876 by two sets of categorization (CLcr and MDRD-based eGFR) of renal function group:

- Individual subject concentration data and summary statistics
- Individual subject plasma PK parameters and summary statistics

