### **8.2.2. Statistical Methodology**

The statistical comparisons of the natural log-transformed PK parameters for GS-9876 between renal impaired subjects and healthy controls will be performed. All subjects with available data for the PK parameter under evaluation will be included in the modeling.

Consistent with using two sets of renal function categorization in PK summaries, two corresponding sets of comparisons will be performed. Details of these comparisons are shown in [Table 8-3](#). To ensure the appropriateness of applications of statistical testing, the comparisons will only be implemented when there are at least 3 subjects in both test and reference groups. The ratio of geometric least squares means (GLSMs) for the PK parameter in comparison between the test and reference groups and the 90% CI for the ratio will be provided.

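### SAP 3.6 imputes a below-quantitation PK parameter as half the assay LOQ, which has the wrong units for AUC and, in the rare case where it acts, would distort the primary AUC ratio

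*SAP*

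**What the plan says.** SAP 3.6, after its display rules for BLQ concentrations, adds a rule at the parameter level: "Pharmacokinetic parameters that are BLQ will be imputed as one-half LOQ before log transformation or statistical model fitting". It does not name the parameters covered, say which LOQ is meant, or explain how a derived parameter comes to be BLQ.

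Protocol 8.1.2 defines the outcomes: "The primary endpoints are PK parameters AUC_{last} , AUC_{inf} , and C_{max} for GS-9876". All three are log-transformed and modelled under SAP 8.2.2.

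Other sections work differently:

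- SAP 8.1 handles BLQ samples when AUC is calculated. They are zero before the first quantifiable sample and missing after it.
- SAP 8.2.1: "Individual PK parameter data listings and summaries will include all subjects for whom PK parameter(s) can be derived".
- SAP 8.2.2: "All subjects with available data for the PK parameter under evaluation will be included in the modeling".
- Protocol 8.3 has a BLQ rule for concentrations only, and only for summary statistics. SAP 2.4 says that no departure from the protocol's analyses is planned.

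The PK Analysis Set in SAP 3.1.3 requires that the subject took study drug and has a postdose concentration result that is not missing. It does not require that result to be quantifiable.

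**The concern.** The LOQ is in ng/mL and AUC is in ng·h/mL, so half an LOQ is not a quantity that AUC can take. Entered as a bare number, it lies so far below any real AUC that on the log scale one subject would determine that group's geometric mean and variance.

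The SAP also gives two answers for the same subject. Under 3.6 a subject with no quantifiable postdose sample enters the model with a constructed value. Under 8.2.1 and 8.2.2 that subject has no derivable AUC and drops out. Two programmers could each follow the SAP and report different primary results. Nothing in the PK Analysis Set definition settles which is meant.

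**Working it through.** **Inputs.** Group size: 8 evaluable and 10 enrolled per group (Protocol 8.8). Log-scale SD: 0.35 (Protocol 8.8). Typical AUC: 2865 ng·h/mL, the predicted 20 mg single-dose exposure (Protocol Table 1-1, note b). Assumed, because the documents give no figure: LOQ 0.1 to 5 ng/mL, and Cmax 100 to 300 ng/mL.

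**1. The plan's own precision figure.** "With 16 (8 per group) evaluable subjects", the 90% CI "would be within (50%, 200%) with over 95% probability", "assuming the expected geometric means ratio of 1.0 and inter-subject SD of no more than 0.35 on a natural logarithm scale". The standard error is 0.35 × √(2/8) = 0.175, and t(0.95, 14 df) = 1.761. With the SD held at 0.35 the CI half-width is 0.308. That leaves 0.693 − 0.308 = 0.385, or 2.2 standard errors, on each side (probability 0.972). Integrating over the sampling distribution of the pooled variance gives 0.966, so the plan's figure reproduces. At 7 per group it is 0.934.

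**2. Units.** Replacing one value in a group of n multiplies that group's geometric mean (GM) by [(LOQ/2)/GM]^(1/n). This takes the replaced subject as otherwise lying at the GM. With LOQ 1 and n = 8, AUC in ng·h/mL gives (0.5/2865)^(1/8) = 0.339, a 2.95-fold shift. With AUC in ng·min/mL (2865 × 60) the shift is 2.95 × 60^(1/8) = 4.92-fold. A valid imputation would not depend on the time unit.

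**3. Size for AUC.**

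| Assumed LOQ (ng/mL) | Distance below GM, ln units (SDs) | n = 8: ratio if impaired / if control | n = 10: ratio if impaired / if control |
|---|---|---|---|
| 0.1 | 10.96 (31.3) | ×0.254 / ×3.93 | ×0.334 / ×2.99 |
| 1 | 8.65 (24.7) | ×0.339 / ×2.95 | ×0.421 / ×2.38 |
| 5 | 7.04 (20.1) | ×0.415 / ×2.41 | ×0.494 / ×2.02 |

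A shift of 2-fold or more needs an LOQ of at most 2 × 2865/2^8 = 22 ng/mL at n = 8, or 2 × 2865/2^10 = 5.6 ng/mL at n = 10.

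**4. Effect on the CI.** Take an illustrative sample of 8 per group at normal quantiles, SD 0.35, true ratio 1.0, with separate group variances as in the SAP model and LOQ 1:

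- no imputation: 1.00 (90% CI 0.73 to 1.36)
- one control imputed: 2.97 (0.38 to 23.5)
- one impaired subject imputed: 0.34 (0.04 to 2.66)
- that impaired subject treated as missing: 0.99 (0.71 to 1.39)

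In simulation with one imputed control, the chance that the CI lies within 50% to 200% falls from about 96% to 0 at LOQ 0.1, 1 and 10.

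**5. Cmax.** At n = 8 and LOQ 0.1 to 5, the shift runs from (100/2.5)^(1/8) = 1.59 to (300/0.05)^(1/8) = 2.97.

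**6. The 2-fold criterion for Cohort 3, if judged on geometric means with the imputed value.** The standard error is 0.35 × √(1/8 + 7/64) = 0.169. With a true ratio of 1.0 and one imputed control, the estimate reaches 2 with probability 87% (LOQ 5) to over 99.9% (LOQ 0.1). At n = 10 and LOQ 5 the probability is about 53%. With a true ratio of 2.5 and one imputed impaired subject, the chance of reaching 2 falls from 90% to about 0.

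**7. The same criterion on arithmetic means.** A near-zero value in one of 8 moves a ratio of 1.0 to about 7/8 = 0.87 or 8/7 = 1.14. A ratio of 2.0 moves to 1.75 or 2.29.

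**The case against.** The strongest reply is that only a concentration can be BLQ, so the sentence can be read as covering Cmax alone, where half the LOQ has correct units. On that reading AUC is left to 8.2.1 and 8.2.2 and the conflict over AUC disappears. This is a sensible reading, but the SAP does not state it. The sentence is plural and unrestricted, and it refers to model fitting, where two of the three modelled parameters are AUCs. Even on the narrow reading, the same subject would be imputed for Cmax and absent for AUC.

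The event is also remote, and this stands. All 17 postdose samples over 120 hours would have to be BLQ after a dose with a predicted AUC of 2865 ng·h/mL. The documents give no basis for a probability, and every shift above is conditional on that event.

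There are partial safeguards. SAP 4.3 allows deviations to lead to exclusion from analysis sets, SAP 8.3 allows a sensitivity analysis without questionable data, and Protocol 4.1 allows replacement of subjects who do not complete PK sampling. A CI as wide as 0.38 to 23.5 would attract attention. But these steps are discretionary, and the SAP 8.3 analysis leaves the primary result in place. In an open-label study the choice would be made after the data were seen.

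Finally, treating the parameter as missing can hide a genuinely low exposure. That is fair, and it is why the subject should be listed with the reason.

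**Conclusion.** Wrong as written, with low severity. The sentence assigns AUC a value in the wrong units and contradicts the derivable-parameter and available-data rules. If it acts on AUC, one subject shifts the GLSM ratio about 2.4- to 3.9-fold at n = 8, or 2.0- to 3.0-fold at n = 10, and the CI no longer informs. These sizes rest on the assumed LOQ range and the predicted AUC. For Cmax the fault is one of influence, not units, and may be below 2-fold.

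The documents do not support three stronger inferences:

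- **That the rule would overturn the decision to open Cohort 3.** Protocol 3.1 speaks of a 2-fold mean difference without naming the type of mean. Protocol 8.5 leaves the matter to a sponsor review, and SAP 2.2 plans no formal interim analysis. Nothing ties the criterion to the GLSM or to this imputation. The effect is material only if geometric means including the imputed value are used. On arithmetic means, only a ratio already close to 2 could cross it.
- **That a missed dose would set the rule off.** SAP 3.1.3 limits the PK Analysis Set to subjects who took study drug.
- **That urine results would distort the primary analysis.** The amount excreted is not among the parameters compared in SAP Table 8-3.

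**What to change.** Delete the sentence from SAP 3.6. Apply BLQ rules to concentrations only, as the rest of SAP 3.6 and SAP 8.1 already do. State that a PK parameter that cannot be derived is missing in the model, and list the subject with the reason so that a genuinely low exposure stays visible.

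The cost is one sentence removed and one clarified, with no change to study conduct or planned enrollment. In the rare case where the rule would have acted, that group's n falls by one. The probability that the CI lies within 50% to 200% is about 0.97 at 8 per group and 0.93 at 7 per group. Losing a subject from one group only falls between the two.
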